3.6 Exploratory Analyses

3.6.1 Healthcare Resource Utilization (HRU)

The magnitude of Healthcare Resource Utilization (HRU) (measured by number of admissions to hospitals and duration of stay; number of admissions to the Intensive Care Unit (ICU) and duration of stay, number requiring respiratory support (using Continuous Positive Airway Pressure [CPAP] or mechanical ventilation) and the duration of use, and the number of supplemental oxygen and the duration of use; number of visiting out-patient facilities (outpatient Emergency Department [ED], urgent care, outpatient clinic); and number of prescription or over the counter [OTC] medications and duration of use) will be summarized by treatment group and reported in 3 time period: through 150 days post dose (on ITT population), after 150 days post dose (on ITT population with Day 151 visit), and through 360 days post dose (on ITT population).

Specifically, following summary tables by treatment group will be used to report the magnitudes of HRU (overall for any reason).

- The number and percent of subjects who have had at least one of the following: hospitalization, ICU admission, requiring respiratory support, requiring supplemental oxygen, or visiting an outpatient facility (for any type of the outpatient facility). Similar summaries will also be provided by respiratory support subtype (CPAP or

mechanical ventilation) and the type of outpatient facility. The percentage will be calculated based on ITT population for time interval through 150 days post dose, on ITT population with Day 151 visit for time interval after 150 days post dose, and on ITT population for time interval through 360 days post dose.

- For each of the medical activities listed above, the total number of the activity for a subject who has had at least one respective event in the reporting time-period will be calculated and summarized by treatment group using descriptive statistics (mean, median, standard deviation [SD], minimum, and maximum).
- The total duration of each of the following (in days) will be calculated accumulatively throughout the reporting time-period and summarized by descriptive statistics (mean, median, SD, minimum, and maximum): hospital stay, ICU stay, use of respiratory support, or use of supplemental oxygen for the subjects who has had at least one of the corresponding activity.

Duration of each hospitalization will be calculated from the admission or deterioration date to discharge date. If the discharge date is missing because of the reason that the subject died in the hospital, the duration of that hospital stay will be calculated by from admission to the minimum of {Death Date, End-of-Study Date}. Total duration of hospitalization is the cumulated days of each hospital stay throughout the reporting time-period.

Similarly, duration of each ICU admission, use of respiratory support, or use of supplemental oxygen will be calculated from start date to stop date or the end date, and the total duration of each medical intervention for a subject is calculated by summing the duration of all occurrences in the time interval of interest.

In addition to the overall HRU summary, the HRU for (1) medically attended RSV LRTI (Protocol-Defined), (2) medically attended non-RSV LRTI (Protocol-Defined), (3) medically attended RSV LRTI (Non-protocol Defined) and (4) medically attended non-RSV LRTI (Non-protocol Defined) will be summarized through 150 days post dose, after 150 days post dose, and through 360 days post dose. The same conventions used for the overall summary (eg, patient population included in a specific summary) will apply for the respective events and the HRU must occur during the event being summarized.

The total number and duration of prescriptions (or OTC medications) related to each of the 4 previously mentioned events per subject through Day 150 post dose will be summarized using descriptive statistics (mean, median, SD, minimum, and maximum) by treatment group. For each treatment group, the average number of prescriptions and duration per event

of interest will also be reported. The average number of prescriptions is calculated by dividing the total number of prescriptions across subjects who have had at least one prescription for the event over the total number of such events over the time interval of interest. The average duration will be calculated similarly. Only subjects with the respective event will be included in the above analysis. Similar summaries will be provided for subjects by RSV hospitalization or non-RSV LRTI hospitalization status (has had at least one or none).

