 - Nasal samples will be collected for all LRTI within 2 days and up to 14 days after the diagnosis. PK and ADA samples will be collected only for subjects hospitalized with LRTI within 2 days and up to 14 days following hospitalization.
 - HRU includes admission and duration of hospital and ICU stay, number of subjects who require respiratory support and supplemental oxygen use, duration of respiratory support and supplemental oxygen use, number and type of outpatient visits (eg, ER, urgent care, outpatient clinic), and number and days of prescription and OTC medication

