4.3.6 Healthcare Resource Utilization and Caregiver Burden Evaluation

Information on HRU and caregiver burden will be collected for all events of medically attended LRTI. This will include admission to and duration of hospital and ICU stay, number of subjects who require respiratory support and supplemental oxygen use, duration of respiratory support and supplemental oxygen use, number and type of outpatient visits (eg, ER, urgent care, outpatient clinic), and the number of prescription and OTC medications and their duration of use. Caregiver burden will be assessed through, for example, caregiver missed work days and the subject’s absence from day care.

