4.8.6 Exploratory Analyses

The magnitude of HRU (eg, number of admissions to hospitals and ICUs and duration of stay; number of subjects who require respiratory support and supplemental oxygen and the duration of use; number and types of outpatient visits, eg, ER, urgent care, outpatient clinic; and number of prescription and OTC medications and duration of use) will be summarized overall by treatment group, and for the following subgroups: subjects with at least one medically attended LRTI caused by RT-PCR confirmed RSV, subjects with medically attended LRTI not caused by RSV, and subjects without medically attended LRTI.

Caregiver burden (eg, caregiver missed work days, subject absence from day care) for subjects with medically attended LRTI caused by RT-PCR-confirmed RSV will be summarized by treatment group.

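### The exploratory HRU tables in SAP v5 are labelled as use for any reason, but the protocol describes HRU collection only for medically attended LRTI events

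*SAP*

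**What the plan says.** **Collection.** Protocol 4.3.6 states: "Information on HRU and caregiver burden will be collected for all events of medically attended LRTI". In Table 4.2.2-1 the HRU row carries a single mark, in the as-needed LRTI column, and none at the scheduled visits or telephone contacts. The table footnote lists the items: "HRU includes admission and duration of hospital and ICU stay, number of subjects who require respiratory support and supplemental oxygen use", followed by outpatient visits and medication. Protocol 3.2.3 gives the purpose as measuring the burden of RSV illness and the resources needed by infants with LRTI.

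**Reporting.** SAP v5 3.6.1 introduces tables that "will be used to report the magnitudes of HRU (overall for any reason"). There are three kinds:

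- Number and percent of infants with at least one hospitalization, ICU admission, respiratory support, supplemental oxygen or outpatient visit: "The percentage will be calculated based on ITT population for time interval through 150 days post dose", with matching denominators for the later periods.
- Counts, restricted to users: "the total number of the activity for a subject who has had at least one respective event in the reporting time-period".
- Durations, also restricted to users, ending with "use of supplemental oxygen for the subjects who has had at least one of the corresponding activity".

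The SAP then adds event-specific summaries for four LRTI categories, the last two being medically "attended RSV LRTI (Non-protocol Defined) and (4) medically attended non-RSV LRTI (Non-protocol Defined) will be summarized through 150 days post dose". It presents these as additional to the overall summary, so the overall summary is meant to cover more than LRTI.

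Protocol 4.8.6 also plans HRU for "subjects with medically attended LRTI not caused by RSV, and subjects without medically attended LRTI". SAP v5 3.6.1 does not list the last of these groups.

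**The concern.** The trigger for collection is narrower than the label on the result. An infant who never has a medically attended LRTI has no described occasion on which an outpatient visit or home oxygen would be recorded as HRU. In a percentage with all ITT infants in the denominator, that infant is counted as not having used the service, when the use was in fact not measured.

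The exploratory objective compares HRU between MEDI8897 and placebo recipients. A reader of a table headed as use for any reason would take it as total healthcare use. What the table could support is a statement about LRTI-associated use. Non-LRTI use, which there is no obvious reason to expect to differ by arm, would be missing from both arms, and the remaining contrast would be the part that prophylaxis is designed to change.

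**Working it through.** **Step 1: described source for each item outside an LRTI event.**

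| Item | Described all-cause source |
|---|---|
| Hospital admission | Yes: inpatient admission makes an AE serious (Protocol 5.2), and SAEs of any cause are collected to Day 361 (5.5.1) |
| Prescription and OTC medication | Yes: all concomitant medication goes in the eCRF (Protocol 4.7) |
| ICU stay, respiratory support | Uncertain: the SAE route would record admissions that involve them, but the documents do not say whether it holds these details |
| Outpatient clinic, emergency, urgent-care visits | None described |
| Outpatient oxygen | None described |

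SAP v5 3.6.1 does not name the source for any row of the overall tables.

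**Step 2: which tables can hold false zeros.** Only number-and-percent uses the ITT denominator. Counts and durations are conditional on use, so no zeros enter them. For items with no other source, they would still describe LRTI episodes only, under the same label.

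**Step 3: illustration of size.** The plan states no HRU figure to reproduce.

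Inputs from the sample-size section (Protocol 4.8.2): placebo RSV LRTI 8% and relative reduction 70%, so MEDI8897 8% × 0.30 = 2.4% and the difference is 5.6 points.

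Assumptions not in the documents:
- Any medically attended LRTI occurs in 25% of placebo infants.
- Only the RSV part differs, so the MEDI8897 figure is 25% − 5.6% = 19.4%.
- Every LRTI involves the service in question.
- A fraction b of infants in both arms uses the service for another reason, independently of LRTI.

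Shown: 25% vs 19.4%, a difference of 5.6 points. Relative reduction = 1 − 0.194/0.25 = 22.4%.

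True share with any use = 1 − (1 − LRTI share)(1 − b). With b = 30%:
- Placebo: 1 − 0.75 × 0.70 = 47.5%
- MEDI8897: 1 − 0.806 × 0.70 = 43.6%
- Difference 3.9 points; relative reduction 3.92/47.5 = 8.3%

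Under these assumptions the true difference is the shown difference times (1 − b).

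**Step 4: range.**

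| Any LRTI, placebo vs MEDI8897 | Reduction shown | True, b = 30% | True, b = 50% |
|---|---|---|---|
| 15% vs 9.4% | 37.3% | 9.7% | 4.9% |
| 25% vs 19.4% | 22.4% | 8.3% | 4.5% |
| 30% vs 24.4% | 18.7% | 7.7% | 4.3% |

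In absolute terms each row moves from 5.6 points to 3.9 (b = 30%) or 2.8 (b = 50%).

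A variant treats RSV LRTI, other LRTI (assumed 10% in both arms) and non-LRTI use as three independent sources. It shows 17.2% vs 12.2% (5.0 points, 29%). The true contrast is 4.5 points (18%) at b = 10% and 0.5 points (0.5%) at b = 90%. The direction is the same throughout, and the size depends almost wholly on b.

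**The case against.** The protocol says that HRU is collected for LRTI events. It does not say that nothing is recorded elsewhere, and the eCRF is not among the documents. If the eCRF captures outpatient visits and oxygen for every illness, the label is correct and only the source is unstated. All-cause routes do exist: SAE records for admissions, including those with ICU care or ventilation, and concomitant-medication pages for drugs. SAP v5 3.5.3 plans to report respiratory hospitalizations that were not LRTI, so the authors expected some data beyond LRTI. This stands: it removes admissions and medications from the problem and leaves ICU stay and respiratory support uncertain.

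Three stronger readings are tempting and are not supported.

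- A reader might infer that all the overall tables are filled with structural zeros. Only the percent table can be; the rule in superseded SAP versions that gave non-users a duration of 0 days is not in v5.
- A reader might infer that SAP v5 itself plans a table for infants without an LRTI. That summary is in Protocol 4.8.6, and its absence from v5 is a separate discrepancy.
- A reader might infer that the plan will overstate the drug's effect on total healthcare use. Section 3.6.1 plans no test, relative risk or relative reduction, and the contrast is inflated only if non-LRTI use is both uncaptured and similar in the two arms.

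Relative reductions also make the gap look larger: in the main illustration the absolute difference falls only from 5.6 to 3.9 points.

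**Conclusion.** The mismatch holds. On the collection that the protocol describes, the SAP v5 percent table would present LRTI-associated use as use for any reason. This is firmest for outpatient clinic, emergency and urgent-care visits and outpatient oxygen, uncertain for ICU stay and respiratory support in non-LRTI admissions, and does not apply to admissions or medications if those are taken from the SAE and concomitant-medication records. The count and duration tables carry the same wrong label for the affected items but hold no false zeros. For those items, the protocol's summary for infants without an LRTI would be empty or zero by construction.

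Whether the contrast between arms is also exaggerated is conditional, and the documents do not fix its size. The figure of 25% vs 19.4% shown against 47.5% vs 43.6% true is an illustration resting on the assumed 25% LRTI rate, 30% other use equal in both arms, and independence. The point concerns an exploratory, descriptive analysis; the primary and secondary efficacy analyses do not use these tables.

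**What to change.** 1. In SAP v5 3.6.1, label as associated with any medically attended LRTI every HRU item whose only source is LRTI-triggered collection, in the percent, count and duration tables alike.
2. Keep the any-reason label only for items with a named all-cause source: hospital admissions from SAE records, medications from concomitant-medication records, and any further item that the eCRF is confirmed to capture for all causes. Check the eCRF before relabelling ICU stay, respiratory support and oxygen, so that valid all-cause data are not discarded.
3. Reconcile Protocol 4.8.6 with SAP v5 on the summary for infants without a medically attended LRTI, and limit it to those all-cause items.

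The cost is SAP wording, table titles and one line in the protocol. No new data are needed. The downside is a narrower exploratory HRU claim.

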3.6.2 Caregiver Burden

Caregiver burden (measured by days of work the caregiver missed, days of daycare/babysitting the subject missed) will be summarized for subjects with medically attended RSV LRTI (Protocol-defined) by treatment group for subjects who have had at least an event in the time-period of reporting. Similar summaries will be provided for medically attended non-RSV LRTI (Protocol-defined), medically attended RSV LRTI (Non-protocol Defined) and medically attended non-RSV LRTI (Non-protocol Defined), respectively. These summaries will be presented through 150 days post dose, after 150 days post dose, and through 360 days post dose using similar reporting convention as described previously.

For each of the events mentioned above and each time-period of reporting, the accumulated total days of work the caregiver missed and the accumulated total days of daycare/babysitting the subject missed will be calculated for each subject and presented using descriptive statistics (mean, median, SD, minimum, and maximum) by treatment group. For each treatment group, the average caregiver burden (i.e., the average number of days of work the caregiver missed, the average number of days of daycare/babysitting the subject missed) for a respective event will be calculated as the total caregiver burden across subjects who has had at least one of the events divided by the total number of the events among these subjects in the time interval of interest. Similar summary will also be provided by the status of hospitalization (at least one or none) that is caused by a respective event mentioned above.

3.7 Safety Analyses

All safety analyses will be conducted on As-treated population.

3.7.1 Adverse Events and Serious Adverse Events

Adverse events will be coded by MedDRA version 19 or higher and the type, incidence, severity and relationship to study investigational product will be summarized by treatment group. Specific AEs will be counted once for each subject for calculating percentages. In addition, if the same AE occurs multiple times within a particular subject, the highest

severity and level of relationship observed will be reported. All treatment-emergent AEs (TEAEs) will be summarized overall, as well as categorized by MedDRA SOC and PT.

Additional summaries will present TEAEs by SOC, high-level term, SOC, and high-level group term. Nontreatment-emergent AEs/serious adverse events (SAEs) will be presented in the listings.

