4.8.4 Safety Analysis

Safety of MEDI8897 will primarily be assessed by the occurrence of treatment-emergent AEs and SAEs. Adverse events will be graded according to the current version of the NCI CTCAE where applicable for pediatric assessments. Adverse events will be coded by

Medical Dictionary for Regulatory Activities (MedDRA) and the type, incidence, severity and relationship to study investigational product will be summarized by treatment group. Other safety assessments will include:

- Occurrence of AESIs to include targeted AEs of hypersensitivity (including anaphylaxis), thrombocytopenia, and immune complex disease (eg, vasculitis, endocarditis, neuritis, and glomerulonephritis) following investigational product administration.
- Occurrence of NOCDs following investigational product administration.

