5.2 Definition of Serious Adverse Events

A SAE is any AE that:

- Results in death
- Is immediately life-threatening

- Requires inpatient hospitalization or prolongation of existing hospitalization
- Results in persistent or significant disability/incapacity
- Is a congenital anomaly/birth defect in offspring of the subject
- Is an important medical event that may jeopardize the subject or may require medical intervention to prevent one of the outcomes listed above

Medical or scientific judgment should be exercised in deciding whether expedited reporting is appropriate in this situation. Examples of medically important events are intensive treatment in an emergency room or at home for allergic bronchospasm, blood dyscrasias, or convulsions that do not result in hospitalizations; or development of drug dependency or drug abuse.

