2.2 Study Design

The population to be enrolled is healthy preterm infants born between 29 weeks 0 days and 34 weeks 6 days GA who would not receive RSV prophylaxis based on the American Academy of Pediatrics (AAP) or other local or national guidelines. These infants will not be receiving palivizumab, allowing for a placebo comparator group for the determination of efficacy and the safety profile. A total of 1,500 infants will be randomized in a 2:1 ratio to receive a 50 mg IM dose of MEDI8897 (N = 1000) or placebo (N = 500). Randomization will be stratified by temperate zones in the northern and southern hemisphere and by subject age group at randomization (ie, ≤ 3 months, > 3 to ≤ 6 months, > 6 months). Enrollment of infants > 6 months of age will be limited to approximately 500. All infants will be followed for approximately 360 days after dosing.

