2.4 Sample Size

The sample size of 1,500 subjects is necessary based on advice from the United States Food and Drug Administration US FDA requesting that 1,000 preterm infants be exposed to MEDI8897 in this Phase 2b study. This sample size has approximately > 99% power to detect 70% relative-risk reduction, assuming a placebo group medically attended RSV LRTI incidence of 8%. Power calculations are based on a Poisson regression model with robust variance (Zou, 2004) comparing MEDI8897 50 mg versus placebo, with 2-sided, $\alpha = 0.05$.

- The 70% relative-risk reduction assumption is based on a placebo-controlled study in Native American infants in which there was 87% relative reduction in the incidence of RSV hospitalization (11.3% placebo; 1.5% motavizumab; $p < 0.001$) and 71% relative reduction in the incidence of outpatient RSV LRTI (10.0% placebo; 2.9% motavizumab; $p < 0.001$) in infants who received motavizumab prophylaxis (O'Brien et al, 2015)

In order to evaluate risk, a sample size of 1,000 subjects exposed to MEDI8897 will provide a 90% probability of observing at least one AE if the true event rate is 0.2%; if no AEs are observed, this study provides 95% confidence that the true event rate is < 0.3%.

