All above stated summaries will be based on observed events and data summary will be presented by Day 150 post dose (on the ITT population), after 150 days post dose (on the ITT population with Day 151 visit), and through 360 days post dose (on ITT population). For subjects with multiple events, only the first occurrence will be used in each relevant incidence summary.

For various medical events, including the primary endpoint, detailed definitions of new onset of events are defined in the following table, Table 3.5-1. For medically attended LRTI (regardless RSV Yes or No, or Protocol-defined Yes or No) the total number of event occurrences for each subject and the percentage of each outcome will be summarized by treatment group on 3 time-intervals: Day 150 post dose (on the ITT population), after 150 days post dose (on the ITT population with Day 151 visit), and through 360 days post dose (on ITT population). In addition, a listing that provides relevant information for subjects with more than one medically attended LRTI event throughout the study will be generated. The listing contains the following information: Age at randomization, Hemisphere, Total number of events, Days post dose, AE verbatim term, Date of AE onset/stop, Days from previous event, Visit setting, Protocol-defined (Y/N), RSV (Y/N), and RSV subtype (when applicable).

Table 3.5-1 Definition for New Onset of Events

Event	Description
New onset medically attended RSV LRTI	A new onset medically attended RSV LRTI will be defined as an adverse event (AE) (for which at least one healthcare visit is associated with RSV LRTI) and occurs at least 14 days (and similarly using 30 days) after the resolution date of the previous AE for a medically attended RSV LRTI.
New onset RSV LRTI hospitalization	A new onset medically attended RSV LRTI hospitalization will be defined as an AE (for which at least one hospitalization is associated with RSV LRTI) and occurs at least 14 days (and similarly using 30 days) after the resolution date of the previous AE for a medically attended RSV LRTI hospitalization.
New onset medically attended RSV outpatient LRTI	A new onset medically attended RSV outpatient LRTI will be defined as an AE (for which at least one healthcare outpatient visit is associated with RSV LRTI) and occurs at least 14 days (and similarly using 30 days) after the resolution date of the previous AE for a medically attended RSV outpatient LRTI.

Table 3.5-1 Definition for New Onset of Events

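### The any-SAE rate by arm will include the RSV hospitalizations the drug is meant to prevent, and no planned table gives the rate of infants with any other SAE

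*SAP*

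**What the plan says.** - **Safety measure.** Protocol 4.8.4: "Safety of MEDI8897 will primarily be assessed by the occurrence of treatment-emergent AEs and SAEs". Protocol 2.2.2 lists four components: all TEAEs, treatment-emergent SAEs, AESIs and new onset chronic diseases.
- **AE and SAE definitions.** Protocol 5.1 makes no exception for efficacy endpoints. Protocol 5.2 makes an AE serious if, among other criteria, it "Requires inpatient hospitalization or prolongation of existing hospitalization". Protocol 5.5.1 collects both from consent to Day 361, which covers the 150-day efficacy window.
- **The endpoint as an AE.** SAP version 5, Table 3.5-1: "A new onset medically attended RSV LRTI will be defined as an adverse event (AE"). Section 3.5.1.5 uses the same link. Section 3.5.2.1 treats RSV hospitalizations as a subset of medically attended RSV LRTIs.
- **Safety tables.** SAP 3.7 uses the As-treated population. Section 3.7.1 says all TEAEs "will be summarized overall, as well as categorized by MedDRA SOC and PT". It also plans severity, relationship and higher-level-term summaries. It does not name a treatment-emergent SAE table by arm; the explicit SAE summary in the SAP is the one by ADA status in 3.8. Nothing in 3.7.1 to 3.7.6 removes RSV LRTI.
- **Tables of the endpoint itself.** Sections 3.5.1.5 and 3.5.3 tabulate AEs associated with RSV LRTI and with all LRTI, on the ITT population.

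**The concern.** If the drug works, the placebo arm has more RSV hospitalizations, and each one is an SAE. The proportion of infants with any SAE then adds together events prevented and any events caused. An excess of other SAEs on MEDI8897 of about the same size as the reduction in RSV hospitalization would leave that row level.

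Safety compared with placebo is a secondary objective, and an acceptable safety profile is part of the primary hypothesis of a study described as pivotal. A reader will want to know how many infants in each arm had an SAE other than the illness being prevented. The planned tables do not give that number. It cannot be had by subtraction, because one infant can have both kinds of event and because the LRTI tables use ITT while the safety tables use As-treated.

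**Working it through.** **1. The plan's own figure.** SAP 2.4 claims "approximately > 99% power to detect 70% relative-risk reduction, assuming a placebo group medically attended RSV LRTI incidence of 8" per cent. So placebo is 8% and MEDI8897 is 0.3 × 8% = 2.4%, with 500 and 1,000 infants. The standard error of the log relative risk is √(0.92/40 + 0.976/24) = 0.252, and ln(0.3) = −1.204, so z = 4.77 and power at two-sided 0.05 is Φ(4.77 − 1.96) = 99.75%. A pooled two-proportion test gives 99.6%. The claim reproduces. The design therefore expects an imbalance of 5.6 points in endpoint AEs inside the safety data.

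**2. Inputs for the any-SAE row.** Let *h* be the placebo risk of RSV hospitalization and *b* the risk of any other SAE. All of the following are assumptions:
- *h* is 1-6%. It cannot exceed 8% under the design, because these hospitalizations are a subset of the primary endpoint. The only hospitalization rates in the documents, 11.3% and 1.5%, come from the cited motavizumab trial in another population and are not used.
- The design's 70% reduction applies to hospitalization too.
- *b* is 3-12%, and the two kinds of event are independent.

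**3. Formulas.** Any SAE on placebo = 1 − (1−b)(1−h). Any SAE on MEDI8897 with no true difference in other SAEs = 1 − (1−b)(1−0.3h). The excess of other SAEs on MEDI8897 that makes the two arms equal is (1−b) × 0.7h / (1−0.3h), which is close to 0.7h whatever *b* is.

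**4. Results.**

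| h | b | Any SAE, placebo | Any SAE, drug, no true difference | Relative risk | Other-SAE rate on drug that is fully offset | Excess (points) |
|---|---|---|---|---|---|---|
| 1% | 3% | 3.97% | 3.29% | 0.83 | 3.68% | 0.68 |
| 1% | 10% | 10.90% | 10.27% | 0.94 | 10.63% | 0.63 |
| 2% | 5% | 6.90% | 5.57% | 0.81 | 6.34% | 1.34 |
| 2% | 12% | 13.76% | 12.53% | 0.91 | 13.24% | 1.24 |
| 4% | 3% | 6.88% | 4.16% | 0.61 | 5.75% | 2.75 |
| 4% | 5% | 8.80% | 6.14% | 0.70 | 7.69% | 2.69 |
| 4% | 8% | 11.68% | 9.10% | 0.78 | 10.61% | 2.61 |
| 6% | 5% | 10.70% | 6.71% | 0.63 | 9.06% | 4.06 |

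The extreme corners of the range are h = 6%, b = 3% (4.75% against 8.82%, relative risk 0.54, offset 4.15 points) and h = 1%, b = 12% (12.26% against 12.88%, relative risk 0.95, offset 0.62 points).

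**5. Any-TEAE row.** Taking the AE proportions of the earlier infant study (Protocol 1.4: 66.7% and 71.8%) as background and 8% against 2.4% for RSV LRTI:
- At 66.7%: 69.4% against 67.5%, a shift of 1.9 points.
- At 71.8%: 74.1% against 72.5%, a shift of 1.6 points.

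Those proportions come from an interim look 30 days after the last dose. A higher background over a full year would shrink the shift further (0.8 points at 85%).

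**6. What the added row could show.** With 500 and 1,000 infants, the power to detect 5.0% against 7.7% at two-sided 0.05 is about 50%; at h = 1% it is below 10%. The row would be descriptive. Its use is that the estimate is no longer mixed with the endpoint.

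**The case against.** Much of the opposing case stands.

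- **Safety is descriptive.** No safety test, relative risk or decision rule is planned. The relative risks above describe what a reader would see in the row; they are not planned statistics.
- **Only an aggregate row is affected.** The tables by SOC/PT and higher-level terms, the relationship, AESI, skin reaction and new onset chronic disease summaries, and the timing tables (within 1 and 7 days of dosing) would show an excess concentrated in another organ class. Protocol Appendix 2 classes an event as not related when a typical disease-related cause is clearly more likely, so the related-event summary should mostly leave out confirmed RSV illness. An independent DMC also reviews safety.
- **Respiratory events are partly separated.** SAP 3.5.3 splits LRTI by RSV and hospitalization status, and 3.6.1 reports hospitalization for any reason and resource use for RSV and non-RSV LRTI. These are ITT tables, however. The overall LRTI summary in 3.5.3 counts each infant once with RSV ranked first, so a second, non-RSV hospitalization in the same infant drops out. None gives the rate of infants with any other SAE.
- **Fewer RSV hospitalizations is a real reduction in SAEs**, so the all-event row is valid as net experience. To call the difference spurious would be wrong.
- **The rates are assumed.** SAEs run to Day 361, while the 8% and 70% concern the first 150 days. Later RSV hospitalizations at equal rates would act as background, moving the relative risk towards 1 but hardly changing the offset.
- **The statistical programming plan is not available** and may already contain such a table.

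A reader might infer that the safety objective is answered with a bias, or that real harm would in general be hidden. The component tables do not support that. An excess would have to be spread thinly across terms, or lie within respiratory and infection terms that mix RSV and non-RSV events, to escape them.

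**Conclusion.** The point holds for the aggregate any-SAE row. The row will contain RSV hospitalizations, which favours the drug, and the SAP supplies no figure for infants with any other SAE. Over the combinations tabulated, its relative risk would read about 0.6 to 0.94 with no difference in other SAEs, and it could offset an excess of about 0.6 to 4 points. These sizes rest on the assumed rates, an equal 70% reduction for hospitalization, and independence. The effect on the any-TEAE row is small.

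A reader might go further and want a table without the endpoint to become the main safety comparison. The documents do not support that: Protocol 2.2.2 and 4.8.4 define safety on all TEAEs and SAEs, and removing RSV illness from the main comparison would hide any worsening of RSV disease. This is a cheap improvement in reporting, not a flaw that undermines the safety assessment.

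**What to change.** In SAP version 5, section 3.7.1:

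1. Keep the all-TEAE and all-SAE tables by arm as the protocol-defined safety summary, and name the treatment-emergent SAE table explicitly.
2. Add a supplementary As-treated table, overall and by SOC/PT, of any SAE, any TEAE and any Grade 3 or higher TEAE, leaving out events linked to a centrally confirmed, protocol-defined RSV LRTI or RSV hospitalization. Exclude events, not infants, so that an infant with both kinds still counts for the other one.
3. State that the two sets are interpreted together.

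The AE link already exists in section 3.5.1.5 and Table 3.5-1. The cost is a few lines of SAP text, one more table set, and a second set of percentages to explain. AE reporting and clinical management do not change.
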